3.3 Efficacy Analyses

Table 3 specifies efficacy analyses types, endpoint, population, statistical model and whether log-transformed data and multiple imputation are needed.

Table 3: Summary of Analysis Methods in Efficacy Analyses for Continuous Efficacy Endpoints

| Endpoint | Analysis Type | Log-Transformed Data | MCMC imputation | Population | Model |
|------------------|------------------------|----------------------|--|------------|---------------------------------------|
| Primary Endpoint | Primary analysis | Yes | Yes, assume MAR | FAS | ANCOVA |
| | Sensitivity Analysis 1 | Yes | Yes, assume MAR | PPS | ANCOVA |
| | Sensitivity Analysis 2 | Yes | Yes, assume MAR | FAS | non-parametric Wilcoxon Rank Sum test |
| | Sensitivity Analysis 3 | Yes | Yes, assume MAR | PPS | non-parametric Wilcoxon Rank Sum test |
| | Sensitivity Analysis 4 | Yes | Yes, Placebo: assume MAR. ISIS Treatment group: | FAS | ANCOVA |

| | | | | | |
|---|--------------------------|--|--|-------------|--------|
| | | | Missing before discontinuation, assume MAR missing after discontinuation assume CIR | | |
| | Sensitivity Analysis 5 | Yes | No | FAS | ANCOVA |
| | Sensitivity Analysis 6 | Yes | No | FAS | MMRM |
| | Subgroup analysis | Yes | Yes | FAS | ANCOVA |
| Secondary Endpoints: ANGPTL3 protein, TC, LDL-C, HDL-C, VLDL-C, Non-HDL-C, ApoB (ApoB-48, ApoB-100), ApoC-III, ApoA-I, FFA, Lp(a) | Secondary analysis | Yes for Percent change from baseline; No for change from baseline | No | FAS and PPS | ANCOVA |
| Other Secondary Endpoints | Secondary analysis | No | No | FAS and PPS | ANCOVA |
| ██████████ ██████████ | ██████████ ██████████ | ██████████ ██████████ ██████████ ██████████ | No | FAS | ANCOVA |
| LDL-C | Subgroup analysis | Yes for Percent change from baseline; No for change from baseline | No | FAS | ANCOVA |

3.3.1 Primary Analyses

3.3.1.1 Primary Endpoint Definition

The primary endpoint is the percent change in fasting triglycerides from baseline to the primary analysis time point. The primary analysis time point is Week 27 for Cohort A, and Week 25 for Cohort B and C. Responses collected at these timepoints will be the endpoints considered in the primary efficacy analysis.

3.3.1.2 Primary Efficacy Analysis

The percent change from baseline in triglycerides will be analyzed using an ANCOVA model with treatment group as a fixed factor and log-transformed baseline triglycerides as a covariate. The ANCOVA model will use $\log(Y/\text{base})$ as dependent variable, where Y is the post-baseline value of triglycerides and base is the baseline value of the triglyceride. The model will provide an estimate of the log ratio, which will then be converted back to the original ratio scale. The percent change from baseline will then be estimated based on the estimated ratio. Patients with missing primary endpoint will have their fasting triglyceride value imputed using the following multiple imputation method described below.

Missing data for the primary efficacy endpoint will be handled by a multiple imputation model that contains the following variables: log-transformed baseline fasting triglyceride value, log-transformed fasting post-baseline triglyceride values, stratified by treatment (Schafer 1997; Schafer 1999). Imputation of missing data will be conducted under a working assumption of missing at random (MAR), meaning that the propensity for a data point to be missing is not related to the missing data, but it is related to some of the observed data.

The imputations will be performed for post-baseline visits. The Markov Chain Monte Carlo (MCMC) method will be used under the multivariate normality assumption to impute the missing primary endpoint by treatment group (ISIS 703802 treatment group or pooled placebo treatment group). In order to be compliant with the normality assumption, baseline and post-baseline triglyceride data will be log-transformed prior to the imputation process. Jeffreys' prior will be used to derive the posterior distribution of the parameters. The MCMC method will impute 100 datasets in order to estimate the treatment effect.

The primary endpoint will be compared between each ISIS 703802 treatment group and the pooled placebo group for each of the 100 imputed datasets. The estimates from the 100 fitted models will be combined to provide an overall estimate, with corresponding CIs and p-value ([Little and Rubin, 2002](#)). Results from the ANCOVA model will be tabulated by ISIS 703802 treatment groups compared to the pooled placebo group.

For fasting triglycerides, all observed values, change from baseline and percentage of change will be summarized by analysis visit using descriptive statistics in FAS.

Mean (SD) percent change over time in fasting triglycerides will be plotted by ISIS 703802 treatment group and pooled placebo group. Waterfall plots of by-patient percent changes from baseline to the primary analysis time point will also be provided.

The primary efficacy analysis will take place after the last patient has completed the primary analysis time point, and the database has been locked.

All primary efficacy data will be provided in data listings.

The primary efficacy analysis will be done using the FAS population.

The sample SAS code for the ANCOVA model can be found below: where the baseline and post-baseline values will be log-transformed first. $\log(\text{post-baseline}/\text{baseline})$ calculated as $\log(\text{post-baseline}) - \log(\text{baseline})$ will be subjected to the ANCOVA model.

```
*****  
  
* Note:  
* Base= baseline  
* Y=Post-baseline  
* TRTP = Treatment group: pooled placebo, 40 mg Q4W, 80 mg Q4W, 20 mg QW  
*****  
  
ods output lsmeans=lsme diff=diff;  
  
proc mixed data = dataset;  
  
    class TRTP (ref='pooled placebo') ;  
  
    model log (Y/base)= TRTP log(Base) /solution cl;  
  
    lsmeans TRTP/ diff cl;  
  
run;
```

3.3.1.3 Sensitivity Analyses of Primary Efficacy Endpoint

Sensitivity Analysis 1 (PPS) – The primary efficacy analysis will be repeated, using the PPS population.

Sensitivity Analysis 2 and 3 (Non-Parametric Analyses) The primary efficacy endpoint will be analyzed using a non-parametric Wilcoxon Rank Sum test using both the FAS and the PPS. Missing data will be handled using the same MCMC multiple imputation method as the primary analysis. The treatment effect will be estimated using the Hodges-Lehmann estimator of the location shift between ISIS 703802 treatment groups and the pooled placebo group. Asymptotic 95% CI and corresponding p-values will be provided.

Sensitivity Analysis 4 (FAS) Using controlled imputations (pattern mixture models [PMM] with ANCOVA) will be conducted to assess the robustness of the missing at random assumption. With this approach, missing not at random (MNAR) is assumed, and the mean function for the missing data

from patients treated with ISIS 703802 who discontinue the study is pre-specified. Missing triglycerides for placebo patients will be imputed using the same MCMC multiple imputation method as the primary analysis. Patients treated with ISIS 703802 who discontinue the study due to AE or lack of efficacy will have their post-discontinuation Triglyceride values imputed using estimates from the placebo patients using the copy increment from reference (CIR) approach, detailed in ([Carpenter et al. 2013](#)). The assumption is based on the premise that when a patient discontinues treatment due to informative missing data, at the time of discontinuation they would progress in a similar manner as placebo-treated patients. Otherwise, non-informative missing data will be imputed using the same MCMC method as the primary analysis, since it is assumed that those patients would have continued in a similar manner to similar patients in their own treatment group who remained on the study. Therefore, the missing data for these patients is expected to be missing at random.

Sensitivity Analysis 5 (FAS) An ANCOVA will be performed on the primary efficacy endpoint (log-transformed) without applying any imputation for missing data.

Sensitivity Analysis 6 (FAS) A repeated measures analyses will be performed on the fasting triglyceride endpoint. The percent change from baseline in triglycerides will be analyzed using an MMRM model with treatment group as a fixed factor, log-transformed (if necessary) baseline triglycerides and timepoint as covariates. If log transformation is applied, the analysis will carry the same conditions as the primary efficacy analysis for back transformation. No imputation of data is applied to this analysis. Visit mapping is provided in Appendix A and SAS code is outlined in Appendix B.

3.3.2 Secondary Efficacy Analyses

All analyses of secondary endpoints will be performed on the FAS as primary and the PPS as supportive. Secondary efficacy analyses will be based on data collected at the primary analysis time point.

- Change and percent change from baseline at the primary analysis time point in ANGPTL3 protein, TC, LDL-C, HDL-C, VLDL-C, Non-HDL-C, ApoB (ApoB-48, ApoB-100), ApoC-III, ApoA-I, FFA, Lp(a) will be compared between each ISIS 703802 group and pooled placebo group using an ANCOVA model without applying any imputation for missing data. In ANCOVA model, $\log(Y/X)$ will be dependent variable, where Y is the post-baseline lipid value and X is the baseline lipid value, log-transformed baseline will be a covariate.
- Change from baseline at the primary analysis time point in fasting plasma glucose, HbA1c, fasting insulin, HOMA-IR, fructosamine and glycated albumin will be compared between each ISIS 703802 treatment group and pooled placebo group using an ANCOVA model with baseline as covariate.
- Change and percent change from baseline at the primary analysis time point in weight, SBP and DBP will be compared between each ISIS 703802 treatment group and pooled placebo group using an ANCOVA model with baseline as covariate.
- Change and percent change from baseline at the primary analysis time point in hepatic fat fraction (HFF) by MRI-PDF will be compared between each ISIS 703802 treatment group and pooled placebo group using an ANCOVA model with baseline as covariate.

- Proportion of patients reaching hepatic fat fraction (HFF) $\leq 8\%$ and $< 5\%$ by MRI-PDFF at the primary analysis time point will be compared between each ISIS 703802 treatment group and pooled placebo group using a logistic regression model with baseline HFF as a covariate.
- Proportion of patients with percent decrease from baseline in hepatic fat fraction (HFF) by MRI-PDFF $\geq 30\%$ and $\geq 25\%$ at the primary analysis time point will be compared between each ISIS 703802 treatment group and pooled placebo group using a logistic regression model with baseline HFF as a covariate.
- Change from baseline at the primary analysis time point in Fatty Liver Index (FLI) will be compared between each ISIS 703802 treatment group and pooled placebo group using an ANCOVA model with baseline as covariate. Equation below will be used for FLI calculation:

$$FLI = \frac{(e^{0.953 \cdot \log_e(\text{triglycerides}) + 0.139 \cdot \text{BMI} + 0.718 \cdot \log_e(\text{ggt}) + 0.053 \cdot \text{waist circumference} - 15.745})}{(1 + e^{0.953 \cdot \log_e(\text{triglycerides}) + 0.139 \cdot \text{BMI} + 0.718 \cdot \log_e(\text{ggt}) + 0.053 \cdot \text{waist circumference} - 15.745})} \times 100$$

Note: Triglycerides in mg/dL; BMI in kg/m²; GGT is Gamma-glutamyl-transferase in U/L; Waist circumference in cm.

- Change from baseline at the primary analysis time point in ALT and AST will be compared between each ISIS 703802 treatment group and pooled placebo group using an ANCOVA model with baseline as covariate.
- Change from baseline at the primary analysis time point in Adipokines and related metabolic markers such as leptin, adiponectin, and if available, phospholipids (e.g. ceramides, sphingolipids, diacylglycerol) will be compared between each ISIS 703802 treatment group and pooled placebo group using an ANCOVA model with baseline as covariate.
- Change from baseline at the primary analysis time point in body composition as measured by single slice MRI of subcutaneous adipose tissue (SAT) and visceral adipose tissue (VAT), waist circumference, WHR (waist-to-hip ratio), and BMI will be compared between each ISIS 703802 treatment group and pooled placebo group using an ANCOVA model with baseline as covariate.

Summary statistics including all observed values, change from baseline and percentage of change by visit will be performed for secondary efficacy endpoints on the FAS except parameters relevant for safety assessments (i.e., glycemic control, body weight, blood pressure, ALT and AST) that will be summarized on the SS.

[REDACTED]

[REDACTED]

[REDACTED]

[REDACTED]

[REDACTED]

[REDACTED]

[REDACTED]

[REDACTED]

[REDACTED]

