#### 5.1 Inclusion Criteria

1. Must have given written informed consent (signed and dated) and any authorizations required by local law and be able to comply with all study requirements
2. Males or females aged  $\geq 18$  and  $\leq 70$  years old at the time of informed consent
3. Plasma TG at Screening  $> 150$  mg/dL and at qualification of  $> 150$  mg/dL
4. Documented history of hepatic steatosis as determined by at least one imaging record (CT scan, MRI, FibroScan, or US) suggesting liver fat  $> 8\%$ , or positive ultrasound at Screening
5. Baseline MRI indicating hepatic fat fraction (HFF)  $> 8\%$
6. Clinically confirmed diagnosis of T2DM
  - a. Hemoglobin A1c  $> 6.5$  and  $\leq 10\%$  at Screening
  - b. On a stable dose of oral glucose-lowering medication (i.e. metformin, sulfonylureas, DPP-4 inhibitors, SGLT2 inhibitors) for at least 3 months before Screening and plan to remain on the same medication for the duration of the study
7. Body mass index between 27- 40 kg/m^2, inclusive, at Screening
8. If taking lipid lowering medication, subjects must be on a stable dose for at least 3 months before first dose of Study Drug and plan to remain on the same medication for the duration of the study

9. Females: must be non-pregnant and non-lactating and either;
  - a. surgically sterile (e.g., tubal occlusion, hysterectomy, bilateral salpingectomy, bilateral oophorectomy) or;
  - b. post-menopausal (defined as 12 months of spontaneous amenorrhea in females > 55 years of age or, in females ≤ 55 years, 12 months of spontaneous amenorrhea without an alternative medical cause and FSH levels in the postmenopausal range for the laboratory involved) or;
  - c. Abstinent\* or;
  - d. if engaged in sexual relations of child-bearing potential, agree to use 2 highly effective contraceptive methods (refer to [Section 6.3.1](#)) from the time of signing the informed consent form until at least 13 weeks after the last dose of Study Drug (ISIS 703802 or placebo)

\* Abstinence is only acceptable as true abstinence, i.e., when this is in line with the preferred and usual lifestyle of the subject. Periodic abstinence (e.g., calendar, ovulation, symptothermal, post-ovulation methods), declaration of abstinence for the duration of a trial and withdrawal are not acceptable methods of contraception

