#### **10.6.3.2 Analysis of Secondary Efficacy Endpoints**

- Absolute and percentage change at the primary analysis time point in ANGPTL3 protein, TC, LDL-C, HDL-C, VLDL-C, Non-HDL-C, ApoB (ApoB-48, ApoB-100), ApoCIII, ApoAI, FFA, Lp(a) will be compared between each AKCEA-ANGPTL3-LR treatment group and pooled placebo group using an ANCOVA model with Baseline as covariate
- Absolute change in fasting plasma glucose, HbA1c, fasting insulin HOMA-IR, fructosamine and glycated albumin will be compared between each ISIS 703802 treatment group and pooled placebo group using an ANCOVA model with Baseline as covariate
- Absolute and percent change in weight, SBP and DBP will be compared between each ISIS 703802 treatment group and pooled placebo group using an ANCOVA model with Baseline as covariate
- Absolute and percent change in hepatic fat fraction (HFF) by MRI-PDFF will be compared between each ISIS 703802 treatment group and pooled placebo group using an ANCOVA model with Baseline as covariate
- Proportion of subjects reaching hepatic fat fraction (HFF)  $\leq 8\%$  by MRI-PDFF at the primary analysis time point will be compared between each ISIS 703802 treatment group and pooled placebo group using a logistic regression model with Baseline HFF as a covariate.

- Absolute change in Fatty Liver Index (FLI) will be compared between each ISIS 703802 treatment group and pooled placebo group using an ANCOVA model with Baseline as covariate
- Absolute change in ALT and AST will be compared between each ISIS 703802 treatment group and pooled placebo group using an ANCOVA model with Baseline as covariate
- Absolute change in Adipokines and related metabolic markers such as leptin, adiponectin, phospholipids (e.g. ceramides, sphingolipids, diacylglycerol) will be compared between each ISIS 703802 treatment group and pooled placebo group using an ANCOVA model with Baseline as covariate
- Absolute change in Body composition as measured by single slice MRI of subcutaneous adipose tissue (SAT) and visceral adipose tissue (VAT), waist circumference, WHR (waist-to-hip ratio), and BM will be compared between each ISIS 703802 treatment group and pooled placebo group using an ANCOVA model with Baseline as covariate

- [REDACTED]

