1.4.2 Secondary Endpoints

Evaluate the effect of ISIS 703802 on changes from baseline to the primary analysis time point for:

- Change and percent change in ANGPTL3 protein, total cholesterol (TC), LDL-C, HDL-C, very low density lipoprotein cholesterol (VLDL-C), non-high density lipoprotein cholesterol (non-HDL-C), apolipoprotein B (apoB (apoB-48, apoB-100)), apolipoprotein C-III (apoC-III), apolipoprotein A-1 (apoA-I), free fatty acids (FFA), lipoprotein(a) [Lp(a)]
- Change in fasting plasma glucose, fasting insulin, HOMA-IR, HbA1c, fructosamine and glycated albumin
- Change and percent change in weight, systolic and diastolic blood pressure (SBP and DBP)
- Change and percent change in hepatic fat fraction (HFF) by MRI-PDFF
- Proportion of patients reaching hepatic fat fraction (HFF) < 5% or ≤8% by MRI-PDFF

- Change in Fatty Liver Index (FLI)
- Change in ALT and AST
- Change in adipokines such as leptin, or adiponectin, and phospholipids (e.g. ceramides, sphingolipids, diacylglycerol)
- Change in body composition as measured by single slice MRI of subcutaneous adipose tissue (SAT) and visceral adipose tissue (VAT), waist circumference, WHR (waist-to-hip ratio) and BMI

[REDACTED]

[REDACTED]

[REDACTED]

[REDACTED]

[REDACTED]

[REDACTED]

[REDACTED]

[REDACTED]

[REDACTED]

1.4.4 *Safety Endpoints*

- AEs
- Vital signs
- Clinical laboratory tests (serum chemistry, hematology, coagulation, urinalysis)
- Electrocardiogram (ECG)
- Use of concomitant medications
- Exposure and Compliance
- Pharmacokinetics (PK) and Immunogenicity (anti-drug antibody formation)

The details on the safety analyses are discussed in section 3.5.

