- A treatment difference in mean liver fat of 4.75% based on a between-patient standard deviation of 3.96% (Tiikkainen et al. 2004) and a two-sample t-test with an unadjusted alpha level of 0.05 with 96% power.

A total of approximately 96 patients (32 patients per cohort, including 24 patients per cohort treated with ISIS 703802) will be randomized to ensure that the efficacy of ISIS 703802 will be adequately characterized in the study.

3.2.6 *Baseline and Endpoint Definition*

For baseline platelet counts, all assessments from central and local labs will be used. For all other lab data, only values obtained from the central or reference lab will be used for baseline definition.

Baseline for triglycerides, ANGPTL3, TC, LDL-C, HDL-C, VLDL-C, Non-HDL-C, ApoB (ApoB-48, ApoB-100), ApoC-III, ApoA-I, FFA, Lp(a), and other lipid measurements is defined as the average of Day 1 pre-dose assessment and the last non-missing measurement prior to Day 1 pre-dose assessment. If 1 of the 2 measurements is missing, then the other measurement will be assigned as the baseline value. If both are missing, then the baseline will be set as missing. Note that if on Day 1, there are multiple pre-dose assessments, then the last assessment with non-missing value will be used as the Day 1 pre-dose assessment.

Baseline for platelets is defined as the average of all central and local lab assessments combined prior to the first administration of Study Drug.

Baseline for ALT and AST is defined as the average of Day 1 pre-dose assessment and the last non-missing measurement prior to Day 1 pre-dose assessment.

Baseline for ECG is the average of the three ECG assessments taken on Day 1 Pre-dose for ECG. If only one or two ECG assessments are available, the single ECG assessment or average of the two ECG assessments will be used. If Day 1 Pre-dose ECG is missing, the averages of the ECGs obtained during the screening visit will be used as baseline.

Baseline for other measurements are defined as the last non-missing assessment prior to the first administration of Study Drug.

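### The comparison of patients reaching HFF <5% names only logistic regression against one pooled placebo group of about 21 to 24, so an empty placebo cell would leave no finite odds ratio and an uninformative Wald test (minor)

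*SAP*

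**What the plan says.** SAP 1.4.2 lists as a secondary endpoint the "Proportion of patients reaching hepatic fat fraction (HFF) < 5% or ≤8% by MRI-PDFF". The 5% cut-off is new in the SAP: protocol 10.1.2 and 10.6.3.2 have only the 8% cut-off, compared with the "pooled placebo group using a logistic regression model with Baseline HFF as a covariate". SAP 3.3.2 uses the same model for <5% and ≤8%, and for two further definitions, a fall in HFF of at least 25% or at least 30%: each active group is set against the "pooled placebo group using a logistic regression model with baseline HFF as a covariate". No exact, penalised or other sparse-data method is named, and neither is the type of test or interval.

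Protocol inclusion criterion 5 requires a baseline MRI showing HFF above 8%. The comparator is a single placebo group pooled over three cohorts (SAP 3.1).

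For continuous HFF, SAP 3.3.2 gives an ANCOVA with baseline as covariate, and Table 3 shows no imputation: "Other Secondary Endpoints | Secondary analysis | No | No | FAS and PPS | ANCOVA". The section also states: "Secondary efficacy analyses will be based on data collected at the primary analysis time point". SAP Appendix A defines a Week 13 MRI window.

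**The concern.** A patient must lose more than three percentage points of liver fat, from any starting point above 8%, to count as a responder at 5%. On placebo this may be rare, and the placebo group is small. If nobody on placebo responds, the logistic likelihood has no finite maximum for the treatment effects. All three doses share the same comparator, so one empty cell removes the odds ratio for every dose that has a responder, and adjusting for baseline HFF does not prevent it. Software then prints whatever estimate and standard error it had reached when it stopped, with a Wald p-value near 1. A strongly positive result could appear null in the planned table. A replacement method would then have to be chosen after seeing the data.

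**Working it through.** **The plan's own figures.** Three cohorts × 8 placebo patients = 24. With 10% dropout, 24 × 0.9 = 21.6, which the plan states as about 21. For liver fat the SAP assumes "A treatment difference in mean liver fat of 4.75% based on a between-patient standard deviation of 3.96" (percent), with 96% power. The standard error is 3.96 × √(2/21) = 1.222, the noncentrality is 4.75/1.222 = 3.89 on 40 df, and two-sided 0.05 gives 96.7%. The stated figure reproduces. With 24 per arm it would be 98.2%. No power is given for any responder endpoint.

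**Chance of an empty placebo cell.** P(0/n) = (1 − p)ⁿ. The placebo rate p is an assumption, because the documents give none.

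| Assumed true rate | P(0/21) | P(0/24) |
|---|---|---|
| 2% | 65% | 62% |
| 5% | 34% | 29% |
| 10% | 11% | 8% |
| 15% | 3% | 2% |
| 20% | 0.9% | 0.5% |

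**What the model returns when the cell is empty.** For 8/21 against 0/21 the unadjusted odds ratio is (8/13)/(0/21), which is infinite. A constructed data set with the SAP's structure (four arms of 21, baseline HFF as covariate, responders 0, 3, 5 and 6) was fitted by maximum likelihood:

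- All three log odds ratios rose by 1 at each iteration while the log-likelihood stayed flat.
- The standard error was 19.6 at iteration 8, 145 at iteration 12 and about 58,000 at iteration 24. By then the Wald p-values were 1.00.
- With one placebo responder instead of none, the same fit converged.

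**How much evidence the Wald test hides.** Unadjusted, against 0/21:

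- Likelihood ratio for 8/21: 2 × [8 ln(8/21) + 13 ln(13/21) − 8 ln(8/42) − 34 ln(34/42)] = 12.99, p = 0.0003. For 4/21 the same formula gives 5.97, p = 0.015.
- Fisher for 8/21: 2 × C(21,8)/C(42,8) = 0.003. For 4/21: 2 × C(21,4)/C(42,4) = 0.107.
- Firth odds ratio (in a 2×2 table this equals adding 0.5 to each cell). For 8/21: (8.5/13.5)/(0.5/21.5) = 27, 95% CI 3.0 to about 3,600, p = 0.001. For 4/21: (4.5/17.5)/(0.5/21.5) = 11, 95% CI 1.07 to about 1,500, p = 0.043.
- Risk difference with Newcombe 95% CI: 38 points (15 to 59) for 8/21 and 19 points (−0.2 to 40) for 4/21.

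In the full four-arm model with baseline HFF (300 simulated data sets, assumed baseline distribution with mean about 16), the median results were as follows.

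| One dose, against 0/21 | Wald p, stopped at 8 or 12 iterations | Likelihood-ratio p | Firth p |
|---|---|---|---|
| 4/21 | 0.71 or 0.94 | 0.014 | 0.042 |
| 8/21 | 0.67 or 0.93 | 0.0002 | 0.0008 |

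**Continuous HFF, for the optional addition.** Suppose 3 of 24 per arm lack an end-of-treatment MRI at random and all have Week 13. The standard error becomes 3.96 × √(2 × (1 − r² × 3/24)/21). For an assumed correlation r of 0.5, 0.7 or 0.9 between Week 13 and end of treatment it is 1.203, 1.184 or 1.159, against 1.222. That is 1.6% to 5.2% lower.

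**The case against.** The empty cell is hypothetical. The placebo rate is assumed, and at 20% or more the chance is below 1%. The SAP does not prescribe Wald inference or rule out a penalised fit, and its introduction allows justified, documented deviations. The likelihood stays informative: the profile lower limit for the unadjusted odds ratio is about 5.4 for 8/21 and 1.9 for 4/21. SAP 3.2.2 requires counts, percentages and denominators, so 0/21 against 8/21 would be visible. The exact Wald values above depend on where iteration stops.

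All of this stands, and it is why the point is minor. It does not remove the gap. At 4/21 the method decides nominal significance (likelihood-ratio 0.015, Firth 0.043, Fisher 0.107, Wald near 1), so the choice should not be left until after unblinding.

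A reader might also infer that the Week 13 HFF data are never used inferentially, or that the complete-case ANCOVA is a serious flaw. The documents do not support either. SAP text after the secondary analyses and a row of Table 3 are redacted, so the absence of a Week 13 model cannot be asserted. The complete-case choice is explicit. An MRI is scheduled at the early-termination visit, and the end-of-treatment window is 61 days wide (Days 153 to 213 in Cohort A, 139 to 199 in Cohorts B and C).

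**Conclusion.** The concern holds for the HFF responder model, chiefly at <5%; the other three definitions are probably less exposed. If placebo has no responder below 5%, the named model gives no finite odds ratio for any active group with a responder, and its default Wald p-value says nothing. How likely this is depends on an unstated placebo rate: roughly one in three at 5%, one in ten at 10%, negligible at 20% or more.

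It would go too far to infer that no inference would be possible, or that the empty cell is to be expected. The first is contradicted by the likelihood-ratio results, and the second has no figure in the documents behind it. These are secondary endpoints in a Phase 2 study, HFF is also compared as a continuous variable (the form that was powered), and the primary triglyceride analysis is unaffected. Severity: minor.

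**What to change.** Before unblinding, state in SAP 3.3.2 that all four HFF responder endpoints (<5%, ≤8%, fall of at least 25%, fall of at least 30%) are analysed by Firth-penalised logistic regression with baseline HFF as covariate, with profile-penalised-likelihood confidence intervals and p-values. Apply it whatever the cell counts; switching only when a cell is empty would make the method depend on the data. Name the Firth test as the governing inference. Report the unadjusted risk difference with a Newcombe interval as descriptive only, since the two can disagree, as they do at 4/21.

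The cost is SAP wording, one procedure option and one table. Firth shrinks the odds ratios slightly, and its upper limit stays very wide when placebo has no responder, so the risk difference is the more readable measure of size.

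Optional: add a sensitivity analysis of continuous HFF, by mixed model for repeated measures or multiple imputation, that includes the Week 13 MRI. The SAP already uses both methods for triglycerides. State that it assumes missing at random, gains little precision, and corrects nothing for patients without a Week 13 MRI.
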